Medication Support. Patients receiving either medication will be given initial and ongoing support to increase understanding of the role of medicine (e.g., foundational and stabilizing, but requiring psychosocial treatment), the medication options, and differences in side effects and risks. Periodic re-evaluation will examine with the patient his/her progress towards goals and, in the event of less than anticipated progress, review the contingency plan (e.g., medication or dose changes, co-occurring disorder management, and escalation of recovery support).

2. Cognitive-Behavioral / Relapse Prevention with Contingency Management: The BHC will deliver manualized cognitive-behavioral relapse prevention (CB/RP) along with contingency management (CM). During Weeks 1-13, patients in the PATH condition will come to the FQHC twice per week for CM and CB/RP sessions. CB/RP will then continue with once weekly sessions in Weeks 14-26, and as needed but tapering in frequency for Weeks 27-52. Procedures for CM and CB/RP are as follows:

Urine Sample Collection and Testing. Patients will be scheduled to provide urine samples twice weekly prior to seeing the LCSW for their regular counseling visits, which will be separated by 2 or 3 days. Samples will be collected under direct observation by a same-sex staff member. Valid samples will be tested for Opioids using quick read test strips at the cutoff levels established by SAMHSA to indicate substance abstinence (specific testing materials to be determined by the FQHC's billing and reimbursement practices). Urinalysis results will be entered into a database that calculates the value of the voucher to be delivered.

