3. Recovery Support Services: Peer Recovery Specialists will work with the BHC to aid the patient in social service needs, help patients stay motivated and connected and begin focusing on personal recovery goals. Patients will set goals with the Peer Specialist and professional SUD treatment team to improve housing and employment, family / social functioning, manage child care, develop supportive relationships and establish a daily routine. The Peer Recovery Specialist will help the patient access community resources, and offer longitudinal peer / relational support. The Peer Recovery Specialist also provides a model of a recovery lifestyle. If a patient goes missing, the Peer Specialist will seek out the patient by telephone or through contacts and re-engage them.

Follow-up Procedures

We will complete follow-up assessment interviews with participants at 3-, 6-, 9-, 12-, 15- and 18-months post-baseline. Follow-up assessments will take place in-person, generally at the FQHC site. If the participant is not able to travel to the FQHC (or they have been discharged and are not allowed back on the premises), then we will meet them in a safe, neutral location such as a restaurant or public library. The assessment battery will be similar to that collected at Baseline (see Item #7), and we will collect a hair and urine sample. If a participant is incarcerated at any follow-up point research staff will not attempt to contact the participant while incarcerated.

We will also call participants every month that a follow-up assessment is not due (i.e. months 1, 2, 4, 5, 7, 8, 10, 11, 13, 14, 16, and 17) to verify the Locator information they provided at baseline, and update any information that has changed.

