Main research trial participants will be compensated \$50 for completing each research assessment (Baseline, 3-, 6-, 9-, 12-, 15-, and 18 month follow-ups). Main trial participants will also be compensated \$5 each month they do not have a scheduled follow-up assessment and they provide research staff with their contact information (Months 1, 2, 4, 5, 7, 8, 10, 11, 13, 14, 16, and 17). In total, participants will be compensated \$410 for completing all study activities. All payments will be in the form of gift cards.

7. Identify the sources of research material obtained from individually identifiable living human subjects in the form of specimens, records, or data.

Measures that are part of the patients' medical record

We will obtain consent from patients to use the clinical data listed below for research. These measures may be part of patients' medical records, and can be linked back to the patient.

Screening Only:

CO-Triage: CONTINUUM™ Triage (CO-Triage™) [31] is a provisional triage tool for alcohol and substance problems, and identifies broad categories of treatment need along the six ASAM Criteria Dimensions. The decision logic in CO-Triage calculates the provisionally recommended ASAM Level of Care which will provide screening cut-offs for pre-eligibility.

Screening and Follow-up (administered at Screening and all Follow-ups):

ASAM Criteria Software: The ASAM Criteria conducts level-of-care matching [32], i.e., to hospital vs. residential vs. intensive outpatient vs. outpatient care settings. This structured interview assesses objective and patient self-report data to produce multi-dimensional problem severity ratings (medical, employment, self-reported alcohol and drug use, family/social, legal, and psychiatric), used to recommend optimal patient outcome at the least restrictive setting or level of care [33,34]. The software yields a standardized recommended level-of-care [35] with good inter-rater reliability [36] and convergent validity [37], as well as a full DSM-IV and DSM-V SUD diagnoses with symptom/criteria counts. Patient-care matching on the ASAM Criteria scales demonstrate predictive validity on client outcomes [38-41]. This instrument is roughly 1100 items and exists as an online assessment tool. Please accept the following link to access information regarding this tool: <http://asamcontinuum.org/>

Measures collected for research purposes only

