The measures listed below are collected for research purposes only and will not become part of patients' medical records. These measures will be stored separately from those collected as part of the medical record, and only TRI researchers will be able to link this data to the patient.

Weekly during Weeks 1 through 6, Pilot Study Only:

Weekly Timeline Followback (TLFB): The TLFB [42] is a structured interview which helps patients recall their substance use to reflect a specified period. Patients are presented with a calendar representing the past 7 days, and the interviewer helps the patient anchor the calendar with memorable events to reconstruct their use (dates, amounts) over the designated period.

Baseline and Follow-up Instruments (administered at Baseline, 3-, 6-, 9-, 12-, 15-, and 18 month follow-ups):

Urine testing: On-site urine drug testing kits (ACON International) rapidly (5-minute) test for cocaine, opiates, amphetamines, methamphetamines, benzodiazepines, cannabis, barbiturates, PCP, and alcohol. Urine testing will be administered at all follow-ups to capture very recent use (i.e. past 3 days).

Hair follicle testing: Hair follicle samples will be sent to an accredited laboratory for testing. Samples generally provide a 90-day window of use, and will be tested for opiates, cocaine, amphetamines, methamphetamines, ecstasy, marijuana, and PCP. If a hair sample of 1.5 inches cannot be provided, urine sampling only will be performed.

Non-Study Medical and Other Services (NSMOS): This questionnaire was adapted from the Treatment Services Review [43,44] for patients in medical settings. The NSMOS counts substance abuse treatment, medical services, visits to medical offices, hospitalizations, and emergency room visits received that were not a part of the assigned treatment.

FQHC / SUD Treatment Program Case Review: Chart review will verify patient self-report of treatment engagement. We will obtain the first version of this data by pulling payment data from funders. We will resolve inconsistencies between patient report and billing data through chart review.

Texas Christian University Treatment Engagement (TCU ENGForm): The TCU ENGForm [45] measures patient therapeutic engagement in and satisfaction with substance abuse treatment. It includes 36 items from four scales representing Treatment Participation, Treatment Satisfaction, Counseling Rapport, and Peer Support, and it takes approximately 10 minutes to complete.

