Quality of Life Enjoyment and Satisfaction Questionnaire – Short Form. The Q-LES-Q-SF [46] is a 16-item self-report measure designed to measure participant enjoyment and satisfaction experienced in various areas of daily functioning.

Risk Assessment Battery (RAB): This 38-item self-report measures past 3-month drug use, injection-related risk behavior, sexual risk, and HIV testing history and results. The RAB shows excellent reliability, and discriminant and predictive validity for seroconversion amongst drug users [47,48].

Chart Review: By prior patient consent, the health centers and SC substance abuse treatment programs will release study patient records for the following information: treatment session attendance, medications prescribed, prescriptions filled, doses received, and results from urinalysis testing.

- 8. Describe characteristics of the subject population, such as their anticipated number, age ranges, sex, ethnic background, and health status. The study should employ a study design with gender and race representation appropriate to the purpose of the research. Strong justification must be provided for exclusion of broad population groups. Identify the criteria for inclusion or exclusion. Explain the rationale for the use of vulnerable populations as research subjects (i.e., prisoners, pregnant women, disabled persons, drug users, children).**

Research participants will be individuals with moderate to severe OUD who are new or existing patients in outpatient primary care settings. Patients will be eligible if: 1) they meet the criteria for Level 1 care, i.e., outpatient treatment, as defined by the ASAM Criteria, and determined for the patient's needs according to the decision engine built into the ASAM Criteria Software, or 2) they meet criteria for Level 2 care (Level 2.0), i.e., intensive outpatient program. Patients will be ineligible if: 1) they have an ASAM

level of care higher than 2.0, 2) if they are under 18 years of age, or 3) they are unable to provide informed consent.

We anticipate that the demographic characteristics associated with the patients will be similar to the characteristics of the patients enrolled in the participating FQHCs. These patients are, on average, 60% female, 68% Black, 10% White, 22% other minorities or more than one race, and 12% Hispanic.

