
Secondary Hypotheses: Relative to those in the SC condition, participants in the PATH condition will demonstrate:

- **Lower rates of service utilization (days of hospitalizations, emergency department visits, residential treatment)**
- **Higher quality of life (Q-LES-Q-SF scores)**
- **Lower rates of HIV risk behaviors (RAB total, sex, and drug risk scores)**

Exploratory Hypotheses: Relative to those in the SC condition, participants in the PATH condition will demonstrate:

- **Improved Employment, Family/Social Functioning, and Psychiatric severity scores on the ASAM Criteria.**

Mixed effects models [2] will be used to compare the treatment conditions on each secondary and exploratory outcome at months 6, 12 and 18. Each model will include terms for treatment condition, time, and their interaction, and the baseline value of outcome measure along with any other necessary covariates. Subgroup analyses similar to those outlined above will be conducted to establish the heterogeneity of the treatment effects. Count data (i.e., service utilization variables) will be analyzed using PROC GLIMMIX specifying a poisson distribution and continuous data (i.e., quality of life, HIV risk scores, and psychosocial severity scores) will be analyzed using PROC MIXED.

Missing values. Missing data will not be an issue for some of the outcomes (i.e., time in treatment). The most important source of missing data in this study is likely to be from participant dropout. We will analyze the data under an intent-to-treat principle in which all participants initially randomized will be included [17]. In addition, mixed effects models will provide valid estimates of intervention efficacy if the missing data are ignorable. We will evaluate the patterns of missing data for each outcome and conduct logistic regression and survival analysis models predicting dropout using client characteristics and accrued measures to determine whether the dropout process is ignorable (i.e. whether missed visits are well explained by observable data). We will examine the impact of missing data by comparing results from models in which missing data are imputed and through pattern-mixture models [18] that examine how responses vary as a function of the pattern of missing data.

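### Secondary and exploratory models use three of the six collected visits, and the Poisson model for hospital days leaves its random effects and standard errors open

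*SAP*

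**What the plan says.** **Visits analysed.** In the SAP, the paragraph after the Secondary and Exploratory Hypotheses says that mixed models will "compare the treatment conditions on each secondary and exploratory outcome at months 6, 12 and 18". Under Primary Hypothesis 1, abstinence is modelled at months 3, 6, 9, 12, 15 and 18.

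**Visits collected.** Protocol item 6, Follow-up Procedures: "We will complete follow-up assessment interviews with participants at 3-, 6-, 9-, 12-, 15- and 18-months post-baseline". Protocol item 7 lists the service-use questionnaire (NSMOS), the Q-LES-Q-SF and the RAB under "Baseline and Follow-up Instruments (administered at Baseline, 3-, 6-, 9-, 12-, 15-, and 18 month follow-ups", and the ASAM interview under "Screening and Follow-up (administered at Screening and all Follow-ups". The RAB entry reads "This 38-item self-report measures past 3-month drug use, injection-related risk behavior, sexual risk". The NSMOS entry ("The NSMOS counts substance abuse treatment, medical services, visits to medical offices, hospitalizations, and emergency room visits received") gives no recall window.

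**Treatment intensity.** Protocol item 6, PATH: "During Weeks 1-13, patients in the PATH condition will come to the FQHC twice per week for CM and CB/RP sessions" and "CB/RP will then continue with once weekly sessions in Weeks 14-26". The voucher schedule has 26 samples, and the counselling description makes HIV risk a topic of the sessions.

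**Count model.** The SAP assigns service-use variables to PROC GLIMMIX with a Poisson distribution. It lists only fixed terms: condition, time, their interaction, the baseline value and other covariates. It names no random intercept or slope, scale parameter, robust standard error or deciding contrast. Random patient effects appear only under Primary Hypothesis 1, as a general advantage of mixed models.

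**The concern.** Half of the scheduled follow-up data on every secondary and exploratory outcome goes unused without explanation. For the RAB this is also a gap in content: the period when PATH is most intensive, and when its sessions address HIV risk, falls outside the HIV-risk comparison. A patient last seen at month 3 gives no outcome to any of these models, although the Missing values section promises to include everyone randomized.

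For hospital days the worry is the validity of one test. Days come in runs within a stay, so a patient's counts vary from visit to visit more than a Poisson model allows. A random intercept absorbs differences between patients but not these bursts; a random slope may absorb them as apparent slope variation. The same data could then give a far too liberal or a very conservative treatment-by-time test, depending on a choice the SAP does not make.

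**Working it through.** The documents give no power, alpha or correlation for these outcomes, so there is no stated figure to reproduce. The correlation of .50 and the 20% final attrition are borrowed from the SAP's power section for Primary Hypothesis 1. Power figures assume a two-sided .05 test.

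**1. RAB coverage.** With three-month recall, months 6, 12 and 18 cover months 3-6, 9-12 and 15-18: 9 of 18 months. Months 0-3, 6-9 and 12-15 are unseen. Months 0-3 hold all 26 voucher samples and 13 × 2 = 26 of the 26 + 13 × 1 = 39 counselling sessions scheduled through week 26.

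**2. Time-averaged effect, constant over time.** Under compound symmetry the variance of the mean of m visits is proportional to (1 + (m − 1)ρ)/m, less ρ² after baseline adjustment. Power on three visits, for an effect with 80% power on six, is Φ(2.802 × √(v6/v3) − 1.96).

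| ρ | v3 | v6 | Reduction | Adjusted reduction | Power on 3 visits (adjusted) |
|---|---|---|---|---|---|
| .2 | .467 | .333 | 29% | 31% | 66% (64%) |
| .5 | .667 | .583 | 12.5% | 20% (.417 to .333) | 75% (71%) |
| .8 | .867 | .833 | 3.8% | 15% | 78% (74%) |

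With monotone dropout of 20% × t/18 and generalized least squares, the adjusted reduction is 23% at ρ = .5 (18% at .8, 33% at .2).

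**3. Linear treatment-by-time term.** Squared deviations of the visit times sum to 72 for months 6, 12 and 18, and to 2 × (7.5² + 4.5² + 1.5²) = 157.5 for six visits. The variance ratio is 72/157.5 = .457, so variance is 54% lower at any ρ under compound symmetry, and 80% power on six visits is 47% on three. If correlation decays by a factor of .5 to .8 per three months, the reduction is 27-42% and power on three visits is 57-67%. The gain is smaller if patients' own slopes vary.

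**4. Patients with month-3 data only.** Linear attrition gives 800 × .20 × 3/18 ≈ 27 lost between months 3 and 6. The figure is 0 if nobody leaves before month 6, and 160 if all attrition falls in that gap.

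**5. Hospital days with no true effect.** The documents give no admission rates or stay lengths, so all inputs are assumed: 800 patients; months 6, 12 and 18; chance of a stay per visit 15%, 10% and 8% for a typical patient, paired with mean stays of 3, 7 and 14 days; logit-intercept SD 1; geometric stays capped at 91 days; linear time; no scale parameter; baseline covariate omitted. There were 534 data sets per setting (Monte Carlo error about ±1.8 points at 5%). False-positive rates at nominal 5%:

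| Model and contrast | 3 days | 7 days | 14 days |
|---|---|---|---|
| Random intercept, treatment × time | 34% | 56% | 68% |
| Random slope, treatment × time | 2.6% | 0.4% | 0% |
| Random intercept, month-18 contrast | 9.0% | 3.7% | 1.1% |
| Random intercept, time-averaged effect | 4.7% | 2.4% | 0.2% |

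With patient-level sandwich errors all three contrasts gave 3.7-5.4%.

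A separate check conditioned on patient totals (3,000 data sets per setting). Over repeated runs the unscaled treatment × time test rejected 31-34%, 55-57% and 67-70%; sandwich errors gave 4.8-6.0%. Single-event counts gave 2% unscaled, so they are not inflated. A within-patient Pearson scale still left 10-14%, so a scale parameter is not a reliable substitute. With time categorical and different assumptions (320 per arm, 5-20% admitted per interval, mean stay 3 or 6 days), the unscaled test rejected 44-77%; the inflation does not depend on linear time.

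**The case against.** The three visits match the plan's own landmarks: weekly counselling ends at week 26, treatment is scheduled for one year, and follow-up ends at month 18. With categorical time and complete follow-up, adding visits leaves the 6-, 12- and 18-month estimates unchanged. The precision gain for the average effect assumes a constant effect, which fits poorly with the argument that months 0-3 are special. Recall is stated only for the RAB; a six-month NSMOS window would close the gap for service use. Imputation and pattern-mixture models are planned, and patients lost before month 3 give no outcome either way. On the counts, the high error rates need assumed stays, a random intercept only and reliance on the interaction, while the hypothesis of lower rates is closer to the time-averaged effect. The SAP also plans checks under different distributional assumptions.

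Much of this stands, and it keeps the point minor. It does not remove it. The landmark estimates survive as contrasts within a six-visit model. The RAB gap follows from the stated recall window. Planned imputation softens only the point about patients last seen at month 3. The SAP neither names a deciding contrast nor rules out the random-intercept-only model, and the interaction is in every model. The Sensitivity analyses section opens with the primary hypotheses and carries only its instrumental-variable analysis explicitly to secondary outcomes, so whether its distributional checks reach these counts is unclear.

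**Conclusion.** The concern holds, as a minor point. Using three of six visits gives up precision that is already paid for: 12.5% of the variance of a constant average effect at ρ = .5 (3.8-29% for ρ from .8 to .2), 20% with baseline adjustment (15-31%), and more for a linear treatment-by-time term. It introduces no bias. The RAB comparison omits half the follow-up, including the whole contingency-management phase. For hospital days, the treatment-by-time test can be far too liberal or very conservative depending on an unstated random-effects choice; the exact rates rest on assumed admissions and stays, but the direction was the same in every multi-day setting tried. The time-averaged effect, single-event counts such as emergency visits, and both primary analyses are not inflated.

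**What to change.** 1. In the SAP's secondary and exploratory paragraph, replace the three visits with months 3, 6, 9, 12, 15 and 18, and report the 6-, 12- and 18-month estimates as contrasts within that model.
2. For hospital days, and for residential treatment if it is counted in days, keep the Poisson mean model, state the random-effects structure, and pre-specify patient-level empirical (sandwich) standard errors. The same edit can name the contrast that tests lower rates, the unit for residential treatment and the period each count covers.

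The cost is two or three SAP sentences and a little more analysis work; no new data are needed. There are two downsides. A time-average would cover months 3-18, so the SAP must say which average it reports. Time contrasts for day counts will have wider intervals than a random-intercept-only Poisson model would give.

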Primary Hypothesis 2: Clients in the PATH condition will demonstrate greater retention in treatment than clients in the SC condition. Retention is widely considered the leading proxy for clinical effectiveness in SUD treatment. A Cox proportional hazards survival analysis [5,6] will be used to determine whether the rate of dropout differs between the two treatment conditions. The analysis will account for right-censored data as some participants may not experience the event (i.e., treatment dropout, defined as absence from treatment for 30 days) during the period of observation. The analysis will include any necessary covariates. To establish the HTE for this outcome, the survival analysis will be repeated for each primary and exploratory subgroup identified above. Models will include a term for the subgroup variable and its interaction with treatment condition. Again, if the interaction term is significant, the treatment effect will be estimated separately at each level of the categorical variable that is used to define the subgroups. We anticipate that the proportional hazard assumption will be met as we expect the typical pattern of dropout in both groups (i.e., high hazard early, low hazard late). We will conduct standard residual-based analyses to evaluate proportionality and, in the event that the

proportional hazard assumption is violated, we will use extended Cox models that include a time-dependent covariate to model the non-proportionality [7]. The analyses will be performed using PROC PHREG.

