Power for the Primary Hypotheses. Power analyses were calculated for the primary hypotheses described above. The power analyses for Primary Hypothesis 1 were calculated following the recommendations of Liu and Wu [8]. The analysis was based on a corrected alpha of .025 (.05/2 primary outcomes), a compound symmetry covariance structure, an estimated abstinence rate of 25% in the SC condition (based on data from our prior study), a correlation between observations on the same patient of .50, and assuming 20% attrition at the final time point. For the smallest subgroup (patients primarily using prescription opioids: $n = 266$; 133 per condition), we will have 80% power to detect an approximately 15% difference in abstinence rates between the conditions (i.e., 25% in control vs. 40% in experimental; OR = 2.0). This projected difference is conservative and based only on the repeatedly demonstrated, similarly scaled differences contingency management yields when compared to standard treatment conditions [9-13]. The smallest detectable differences for the remaining subgroups and the overall sample are as follows using the same specifications: (1) patients recruited from IP setting ($n = 400$): 12%, OR = 1.8, (2) patients recruited from OP setting ($n = 400$): 12%, OR = 1.8, (3) patients primarily using heroin ($n = 534$): 9%, OR = 1.6, and (4) the overall sample ($n = 800$): 8%, OR = 1.5. The power analyses for Primary Hypothesis 2 were calculated following the recommendations of Lakatos [14]. The analysis was based on a corrected alpha of .025, no attrition as chart data will be available for all patients, and estimated dropout rate of 60% in the SC condition [15]. For the smallest subgroup (patients primarily using prescription opioids: $n = 266$; 133 per condition), we will have 80% power to detect a hazard ratio of .59 which corresponds to a difference in survival rates of approximately 18% between the two conditions. The smallest detectable hazard ratio for the remaining subgroups and overall sample are as follows using the same specifications: (1) patients recruited from IP setting ($n = 400$): HR = .65, 15% difference in survival (2) patients recruited from OP setting ($n = 400$): HR = .65, 15% difference in survival (3) patients primarily using heroin ($n = 534$): HR = .69, 13% difference in survival, and (4) the overall sample ($n = 800$): HR = .74, 10% difference in survival. We have chosen to use an alpha level that corrects for the number of primary hypotheses rather than the number of subgroup analyses as the latter approach would substantially increase the likelihood of making a type 2 error [4,16].

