Sensitivity analyses . We will conduct a series of sensitivity analyses for the primary hypotheses as recommended by Thabane et al. [19]. We will examine the influence of outliers (identified through boxplots and z-scores) by comparing results from analyses with and without the outlying values. We will examine the impact of protocol non-compliance by comparing the results from the intent-to-treat analyses to analyses in which only participants who received a sufficient dose or different components of the intervention are included; protocol adherence will be represented by weekly medication adherence scores, weekly counseling scores, and combined scores for the sensitivity analyses calculated from TSR and chart review. Furthermore, we will extend the models described above for our primary and secondary outcomes using instrumental variable approaches. Here, the instrumental variable is treatment condition and, under some conditions, will control for unmeasured bias (due to participants self-selecting to comply or not) when estimating the relative effects of the interventions in those who adhere to their assigned intervention. Thus, the results will use data from all subjects who show various degrees of compliance and will yield estimates of the intervention effects that would have been seen in a study with full compliance. For a single overall measure of compliance, the methods of Nagelkerke et al. [20] will be used; if there is sufficient within-subject variation across time in compliance, the longitudinal methods of Small et al. [21] will be used. These sensitivity analyses allow us to determine whether estimates of effect from the primary models can be reported without explicit adjustments for protocol non-compliance. We will examine the impact of our distributional assumptions by comparing results obtained under different distributional assumptions (e.g., parametric vs. non-parametric). We will use multiple imputation and pattern-mixture models to evaluate the impact of missing data as discussed in the prior section. Finally, we will examine the impact of using different definitions of outcomes (e.g., different cutoff points for binary outcomes, objectively verified vs. self-reported substance use) by comparing results obtained from models using different operationalizations of the

outcome variables. These sensitivity analyses will allow us to evaluate the robustness of the study results.

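### The sufficient-dose and full-compliance analyses are planned for retention (Primary Hypothesis 2) too, where the compliance scores overlap heavily with the outcome, so they cannot test its robustness

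*SAP*

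**What the plan says.** The scope is set at the start of the SAP's Sensitivity analyses section: "We will conduct a series of sensitivity analyses for the primary hypotheses". The non-compliance check there compares intent-to-treat with "analyses in which only participants who received a sufficient dose or different components of the intervention are included". Adherence is to be represented by "weekly medication adherence scores, weekly counseling scores, and combined scores for the sensitivity analyses calculated from TSR and chart review". The section then states that "we will extend the models described above for our primary and secondary outcomes using instrumental variable approaches", with treatment condition as the instrument, to "yield estimates of the intervention effects that would have been seen in a study with full compliance". These results have a decision role: they are to show whether the primary estimates may be reported without explicit adjustment for non-compliance. Neither step excepts Hypothesis 2, and no threshold for a sufficient dose is given for either arm.

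Under Primary Hypothesis 2 the SAP defines the event as "treatment dropout, defined as absence from treatment for 30 days". Its power section assumes "no attrition as chart data will be available for all patients", so charts are the working source for retention. Protocol item 7 (Chart Review) lists session attendance and doses received among the chart items.

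**The concern.** For Hypothesis 1 the outcome is hair- and urine-confirmed abstinence, which is measured separately from treatment received. Asking how the effect varies with treatment received is then meaningful. For Hypothesis 2 the outcome is staying in treatment. A patient who leaves accrues no further counseling score, so a low dose is largely a consequence of early dropout.

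Two things follow. Restricting to a sufficient dose selects on the outcome. And an estimate of retention under full compliance asks how often patients leave treatment when they do not leave it. Retention is one of only two primary hypotheses. Results of this kind, used as the SAP intends, could make a real effect look fragile or a null effect look strong.

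**Working it through.** **1. The plan's own figure.** Inputs from the SAP power section: SC dropout 60%, HR .74, n = 800, alpha .025. Protocol item 4 gives 400 per condition. Sidedness is not stated; two-sided is assumed, because it is the reading that reproduces the plan.

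- Expected events = 400 × .60 + 400 × (1 − .40^.74) = 240 + 197 = 437.
- Schoenfeld power = Φ(√(437/4) × |ln .74| − 2.241) = Φ(3.147 − 2.241) = .82.
- Survival difference = .40^.74 − .40 = .508 − .400 = .108.

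The plan states 80% power and a 10% difference, so its retention power is sound. A one-sided .025 would give .88.

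**2. Equal dose cut-off in both arms.** The SAP gives no curve or cut-off, so both are assumptions. SC retention is taken as 60% at week 13 and 40% at week 52. This matches the 60% dropout and the SAP's expectation of a high early hazard. The 52 weeks come from PATH's one-year course in protocol item 6. The cut-offs are illustrative analysis thresholds only.

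- S(t) = .60^(t/13) up to week 13, then .60 × (.40/.60)^((t − 13)/39).
- Events kept at cut-off c, true HR .74 throughout = 400 × [S(c) − .40] + 400 × [S(c)^.74 − .40^.74].
- Example, c = 13: 400 × (.600 − .400) + 400 × (.685 − .508) = 80 + 71 = 151, and 151/437 = 35%. Power = Φ(√(151/4) × .301 − 2.241) = Φ(−.39) = .35.

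The last column uses a different truth: all PATH benefit falls in weeks 1–13. An HR of about .62 in those weeks and 1.00 afterwards gives an overall Cox HR of .75.

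| Cut-off (weeks) | Events kept | Share | Power, HR .74 throughout | Restricted HR, early benefit only |
|---|---|---|---|---|
| none | 437 | 100% | 82% | .75 |
| 4 | 335 | 77% | 70% | .79 |
| 8 | 246 | 56% | 55% | .85 |
| 13 | 151 | 35% | 35% | 1.0 |
| 26 | 95 | 22% | 22% | 1.0 |

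With a constant HR the restricted HR stays at .74, so only precision is lost. With an early benefit the HR moves toward 1. It reaches 1.0 once the cut-off is at or past the week where the assumed benefit ends.

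**3. Unequal cut-offs, no true effect.** Constant hazard, S(t) = .40^(t/52), true HR 1.00.

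- Only PATH restricted to at least 13 weeks: PATH dropout is 1 − .40^(39/52) = 50% against 60% in SC, and the Cox HR is about .68.
- Only PATH restricted to at least 26 weeks: PATH dropout is 1 − .40^(26/52) = 37%, and the HR is about .43.
- SC at least 13 and PATH at least 26 weeks: HR .61.
- SC at least 17 and PATH at least 13 weeks: HR 1.16.

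Retained PATH patients cannot have an event before the cut-off, while SC patients can.

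**4. Full-compliance contrast.** Take compliance D as the share of weeks in treatment and the outcome Y as the share of the year retained. The Wald estimate is [mean Y(PATH) − mean Y(SC)] / [mean D(PATH) − mean D(SC)]. With Y = D this is 1 for any non-zero effect and undefined at no effect, so it carries no information. This is a simplification, because the SAP does not say how the instrumental-variable extension of the Cox model would be done.

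**The case against.** A reader might infer that dose and retention are one record and that retention under full compliance is 100% in both arms by definition. The documents do not support that. The adherence scores include medication and draw on TSR as well as charts. Protocol item 10 leaves medication to the choice of patient and provider, so a patient can attend without taking it. Protocol item 6 makes late counseling as needed in PATH and later outpatient care as needed in SC, and it schedules injections 30 days apart, give or take 7. A patient following the schedule could therefore have a 30-day gap. The overlap is heavy, not complete.

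A reader might also infer that restriction must discard most events or erase a true benefit. That depends on the cut-off: 4 weeks keeps 77% of events, and an early-benefit HR moves only from .75 to .79. Lower power in a sensitivity analysis is also not bias.

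One of the two cited instrumental-variable methods is, by its title, for random-effects logistic models, so abstinence may have been the main target. The SAP does not say so, and its wording covers the retention model. The SAP also already plans to vary outcome definitions, so part of the remedy is present.

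These points limit the strength of the claim. They do not make dose restriction informative about retention.

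**Conclusion.** The point holds as a defect of scope. As written, the SAP restricts and adjusts the retention analysis on scores that overlap heavily with the outcome, then uses the result to judge the primary estimate.

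The direction and size of the distortion are not fixed, because no dose rule is defined. Equal cut-offs cost precision under proportional hazards and dilute an early benefit. Restricting PATH alone can manufacture an effect (HR .68 or .43 when the truth is 1.00). All these figures rest on the assumed curves and cut-offs.

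The intent-to-treat retention test, its alpha and sample size, and the stated detectable hazard ratios are unaffected. The same compliance analyses are not circular in this way for Hypothesis 1.

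**What to change.** In the SAP's Sensitivity analyses section:

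- Limit the sufficient-dose and instrumental-variable analyses to Hypothesis 1 and the secondary outcomes.
- State that no dose or compliance measure that counts attendance or time in treatment will be used to restrict or adjust the retention analysis.
- Assess robustness of Hypothesis 2 by varying the outcome definition, for example with other absence windows, or billing against chart data. Protocol item 7 already provides for both of these sources.

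This takes a sentence or two of SAP wording, reduces the analysis work and changes no power figure. The cost is that no compliance-adjusted retention estimate will be reported.
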